1.1 Synopsis

Sponsor: Massachusetts General Hospital	Protocol Number: B17-166
Name of Study Drug: Glecaprevir (ABT-493), Pibrentasvir (ABT-530)	Phase of Development: 4
Name of Active Ingredient: ABT-493, ABT-530	Date of Protocol Synopsis: October 09, 2018
Protocol Title: A Multi-Center, Open-Label Study of glecaprevir/pibrentasvir to Treat Recipients of Transplanted Kidneys from Deceased Donors with Hepatitis C Virus (MYTHIC: Multi-center studY to Transplant Hepatitis-C InfeCted kidneys)	
Objectives: The primary objective of this study is to demonstrate the safety and efficacy (sustained viral response 12 weeks post treatment [SVR12]) of an 8-week treatment with glecaprevir/pibrentasvir (G/P) in Hepatitis C Virus (HCV)-negative recipients who received study eligible HCV RNA-positive kidneys in Arm 1. The secondary objectives are: 
1) Among all subjects enrolled in the study, to describe time to kidney transplant and cumulative incidence of each type of transplant: a study-eligible HCV RNA-positive kidney (Arm 1), a study-eligible HCV RNA-negative/HCV antibody-positive kidney (Arm 2A), or a kidney transplant performed as part of standard of care treatment (Arm 2B).2) To describe clinical outcomes while on the waitlist after consent (Serious Adverse Event [SAEs], delisting from waitlist, death) between those who receive a study-eligible HCV RNA-positive kidney (Arm 1) and in subjects consented for this study who do not receive a study-eligible kidney transplant from an HCV RNA-positive donor (all Arm 2 subjects) overall and with breakdown by the 3 categories of Arm 2 as below: 
A: subjects who receive a kidney from a study-eligible HCV RNA-	

negative/HCV Ab-positive donor

B: subjects who receive a standard of care kidney transplant

C: subjects who were not transplanted within 1 year of consent

Hereafter, these categories will be referred to as Arms 2A, 2B and 2C.

A “standard of care” transplant will be defined as any of the following kidney transplants: a deceased donor HCV RNA-positive kidney transplant that did not meet donor criteria for Arm 1 or HCV RNA-positive kidney transplant that place after last transplant allowed for Arm 1 but met criteria for Arm 1 inclusion (2B1); a deceased donor HCV RNA-negative/HCV Ab-positive kidney transplant that either did not meet donor criteria or took place > 6 months after the last Arm 1 transplant (2B2); a deceased donor HCV RNA-negative/HCV Ab-negative transplant at a MYTHIC clinical site (2B3); any living donor kidney transplant at a MYTHIC clinical site (2B4); or any kidney transplant at a different center than the 7 clinical sites (2B5).

In addition, to compare the total number of inpatient hospital days while on the waitlist and after study consent in those who did receive a study-eligible HCV RNA-positive kidney (Arm 1) vs total inpatient hospital days in those who did not (Arm 2) overall and with breakdown by the 3 categories of Arm 2 (2A, 2B and 2C).

- 3) To describe clinical outcomes and data post-transplant (death, graft failure, acute allograft rejection, delayed graft function, estimated glomerular filtration rate [eGFR], proteinuria, ALT elevation > 5 times the upper limit of normal (ULN), SAEs) between those who receive an HCV RNA-positive kidney (Arm1) and in subjects who receive an HCV RNA-negative/HCV Ab-positive kidney allograft (Arm 2A) or a standard of care kidney transplant (from Arm 2B1 – 2B4) combined and separately. For subjects of Arm 1 and Arm 2A who become HCV infected, we will collect additional clinical outcomes of sclerosing cholestatic hepatitis and extrahepatic manifestations of HCV. In addition, the clinical


outcomes and data post-transplant will be compared between Arm 1 and Arm 2 where a) any study drug (G/P) related severe treatment emergent adverse events are included as a clinical outcome for Arm 1 and b) all events of treatment emergent Grade ≥ 3 laboratory values and severe G/P-related treatment emergent adverse events are included as clinical outcomes for Arm 1.
 
4) To compare time to deceased donor kidney transplantation among all patients who enrolled in this MYTHIC trial to transplant candidates from the Organ Procurement and Transplantation Network (OPTN) database; MYTHIC participants will be matched 1:3 to OPTN patients on demographics and characteristics known to influence waiting time including waiting list priority, blood group, geographic region, and sensitization.

Investigators: Multi-center, names on file with sponsor

Study Sites: Up to 7 sites

Study Population: HCV-negative subjects wait-listed for a kidney transplant

Number of Subjects to be Enrolled: Up to 90, including a target number of 30 kidney transplantation events from study eligible HCV RNA-positive kidney donors.

Methodology:
 
This is an open-label, multi-center, two-arm study to evaluate the efficacy and safety of fixed-dose combination tablets of glecaprevir/pibrentasvir (G/P) in HCV-negative subjects who consent to receive a kidney transplant from an HCV RNA-positive deceased kidney donor. 90 subjects will be consented for trial participation, out of whom 30 subjects at up to 7 sites are planned to receive an HCV RNA-positive kidney meeting study criteria and will be enrolled into a post-transplant treatment arm (Arm 1) receiving open-label G/P for 8 weeks post-transplant. The remaining enrolled subjects including those who do not receive a kidney meeting study criteria from an HCV RNA-positive donor will be followed in Arm 2 for the minimum duration of 1 year post-enrollment. Arm 2 includes subjects who do not receive a kidney at one of the study sites or who receive a standard of care kidney transplant (Arm 2B5 patients will be censored at the time of transplant at a non-study site). For subjects enrolled in Arm 1 of the study, the

first dose of G/P will be given as early as 3 days post-transplant. Patients must be out of the ICU, able to eat and drink, and take oral medications, so that G/P treatment can be safely initiated orally as judged by the site investigator.

Subjects who are transplanted with kidneys from HCV RNA-positive donors in Arm 1 will be followed for 1 year after the date of transplantation to evaluate safety, graft survival, mortality, allograft rejection, and potential hepatic and extrahepatic manifestations of HCV infection. All recipients of Arm 1 HCV RNA-positive kidneys will be assessed for SVR-12 after G/P treatment. Scheduled visits for subjects who accept an organ from HCV RNA-positive donors in Arm 1 and receive G/P treatment will consist of screening, day of transplant, day 1 of G/P treatment, week 1, week 2, week 4, week 6 and week 8 of treatment (planned end of treatment visit) after starting G/P. Additional scheduled visits will take place at weeks 4, 12 and 24 following completion of the G/P treatment and week 52 (1 year) after transplant. Subjects treated with G/P who experience virological failure will be evaluated for the emergence/persistence of direct-acting antiviral agent (DAA)-resistant viral variants, and suitable retreatment will be offered to study participants.

All subjects in study arm 2 will be followed for a minimum of 1 year from enrollment. In addition, subjects in study arm 2A who received a kidney from an HCV RNA-negative/HCV Ab-positive donor will be followed for a minimum of 24 weeks after the date of transplantation or 1-year post enrollment, whichever is longer, to evaluate safety, graft survival, mortality, and allograft rejection, and potential development of HCV viremia. Study visits for patients receiving a HCV RNA-negative/HCV Ab-positive kidney transplant in Arm 2A will take place at weeks 1, 4, 8, 12, and 24 weeks after transplantation. If a recipient of an HCV RNA-negative/HCV antibody-positive kidney in Arm 2A develops HCV infection within the first 24 weeks of follow-up after transplantation, that recipient will be offered treatment with G/P for 8 weeks. G/P treatment will be administered and subject will be followed as per local transplant center

standard-of-care and study-objective pertinent data from the G/P treatment period and post treatment period will be collected. This includes SAEs, treatment-emergent Grade 3 or greater laboratory abnormalities, and HCV RNA 12 weeks post G/P treatment completion.

Other subjects in Arm 2 who remain on the transplant waiting list, receive a standard of care kidney transplant at a study site (Arms 2B1 - 2B4) will be followed as per transplant center standard of care for at least 12 months post-enrollment with study-objective pertinent collection of data during waitlist period and/or related to transplant events which may include transplant-related complications and graft function, SAEs, delisting from the transplant wait list and death.

Efficacy and safety data will be monitored throughout the study for all participants. However, the approach to surveillance for adverse events will be customized for patients on the waiting list and after transplantation.

Inclusion Criteria for Kidney Transplant Candidates at Enrollment

1. Age >21 and <65 years at the time of consent
2. Estimated glomerular filtration rate (eGFR) < 15 ml/min/1.73 m² (calculated using the 4-variable Modification of Diet in Renal Disease [MDRD] equation) at the time of consent
3. Listed for an isolated kidney transplantation
4. Subjects must be able to understand and adhere to the study visit schedule and all other protocol requirements, and must voluntarily sign and date an informed consent
5. No available medically acceptable, compatible living kidney donor
6. Subject must agree to use an effective method of birth control as outlined in Appendix D, and must have implemented the method by the day of transplant
7. Assent from the patient's primary transplant nephrologist that participation would be reasonable for the patient

8. Attended an educational session on use of HCV seropositive allografts

Exclusion Criteria for Kidney Transplant Candidates at Enrollment

1. History of severe, life-threatening or other significant sensitivity to immunosuppressants utilized in kidney transplant.
2. Female who is pregnant, breastfeeding, or is planning to become pregnant during the study
3. Human immunodeficiency virus (HIV) RNA-positive or HIV antibody-positive
4. HCV RNA-positive
5. Hepatitis B Virus (HBV) surface Ag-positive or detectable HBV DNA
6. Primary focal segmental glomerulosclerosis (FSGS) or disease process with increased risk of causing early graft failure as assessed by the transplant nephrologist and/or investigator team
7. Presence of clinically significant liver disease evident after review of history, labs and fibroscan imaging
 - a) Persistently elevated liver enzymes (Alanine aminotransferase [ALT] >2 times upper limit of normal) of unknown cause
 - b) Liver fibroscan result >8kPA, or >F2 on liver biopsy
8. Transplant candidate requiring antibody desensitization protocol for transplantation
9. Most recent calculated panel reactive antibody (cPRA) $\geq 80\%$. For this purpose, the cPRA assessed will be the cPRA most-recently reported to United Network of Organ Sharing (UNOS) at the time of wait listing.
10. Prior recipient of a non-renal solid organ transplant
11. Subject has any other medical condition that, in the opinion of the Investigator, would adversely affect the participant's participation in the study. Additionally, the investigator may exclude any patient with a pre-existing cancer that does not have a high probability of cure or control and as per local transplant center guidance.
12. Requirement for and inability to safely discontinue the medications or

supplements listed in Table 7 of the protocol at least 2 weeks or 10 half-lives (whichever is longer) prior to the first dose of any study drug
 
13. Participation in another interventional study of any investigational agent or approved medication, or participation in another interventional study that the responsible investigator deemed to be an exclusion, from 6 months prior to screening to the last study visit.
	

Inclusion criteria for kidney donor and allograft*
 
 1. Deceased donor organ with kidney donor profile index (KDPI) ≤ 0.85 2. HCV RNA-positive 
Exclusion criteria for HCV RNA-positive kidney donor and allograft
 
 1. Known prior HCV treatment with direct acting antiviral medication 2. HIV RNA-positive 3. HBV Surface antigen-positive or HBV DNA-positive 
*Standard of care deceased or living donor kidney transplants are allowed to be accepted by enrolled subjects. For HCV RNA-negative/HCV antibody-positive donor offers in Arm 2A, all other donor inclusion and exclusion criteria above apply, except the donor is not HCV RNA-positive. For subjects who accept a standard of care transplant (Arm 2B), no study allograft criteria apply.
	
Investigational Product:	Glecaprevir/pibrentasvir 100 mg/40 mg Film-coated Tablet
Doses:	Glecaprevir Dose: 300 mg QD Pibrentasvir Dose: 120 mg QD Glecaprevir/pibrentasvir tablets: 300 mg/120 mg QD (3 tablets)
Mode of Administration:	Oral once daily with food
Reference Therapy:	N/A

Duration of Treatment:

Treatment duration is 8 weeks

Criteria for Evaluation:

Efficacy:

Efficacy will be assessed by plasma HCV RNA levels after start of G/P treatment

DAA Resistance:

The following resistance information will be analyzed for Arms 1 or 2A kidney transplant recipients receiving G/P who experienced virologic failure and who have a sample from time of failure with HCV RNA ≥ 1000 IU/mL after failure. The HCV NS3 and NS5A amino acid sequences from the sample closest in time after virologic failure or treatment discontinuation will be determined by population sequencing or next generation sequencing, and a listing by subject of all substitutions at GLE and PIB signature amino acid positions relative to the appropriate prototypic reference sequence of NS3 and NS5A will be provided.

Safety:

Separate safety data will be collected for patients while on the waiting list and after transplantation. Because subjects are unlikely to suffer adverse events related to study participation while on the waiting list, adverse event ascertainment will take place every two months by phone as well as during an in-person evaluation every 6 months while on the waiting list. The following clinical outcomes will be collected from all subjects while on the waiting list: SAEs, hospital days, delisting from waitlist, death.

For all transplanted subjects in Arm 1 or Arm 2, the following data will be collected and analyzed descriptively post-transplant: death, graft failure, acute allograft rejection, delayed graft function, eGFR, proteinuria, ALT elevations greater 5 times upper limit of normal, and SAEs. For transplanted subjects of Arm 1 and Arm 2A of the study who develop HCV viremia, the additional data of potential sclerosing cholestatic hepatitis and extrahepatic manifestations of HCV will be collected.

The analysis of adverse events after kidney transplantation will include categorization of the event as to whether the event was caused by transplantation or its treatment generally, or caused by HCV infection and/or HCV therapy as applicable.

All subjects who receive at least one dose of G/P in Arm 1 will have additional safety data collected including treatment-emergent adverse events of all grades, physical examinations, clinical laboratory tests, and vital signs.

Statistical Methods

Efficacy:

The primary efficacy endpoint is sustained virologic response 12 weeks post dosing (SVR₁₂), defined as HCV RNA < LLOQ 12 weeks after the last actual dose of G/P. The SVR₁₂ rate will be determined from all enrolled subjects who received an HCV RNA-positive kidney in Arm 1 and received at least one dose of G/P study drug along with a two-sided 95% confidence interval. The confidence interval for the SVR₁₂ rate will be calculated using Wilson's score method.

The secondary efficacy endpoints for recipients of kidney transplants from HCV RNA-positive donors in Arm 1 are:

1. The percentage of subjects with on-treatment virologic failure;
2. The percentage of subjects with post-treatment virologic relapse.

Additional efficacy analyses will be performed.

Clinical endpoints:

Secondary endpoints for the secondary objectives are:

1. Among all subjects enrolled in the study who receive a kidney transplant, the time to kidney transplant and cumulative incidence of each type of transplant will be determined for: study-eligible HCV RNA-positive kidneys (Arm 1), study-eligible HCV RNA-negative/HCV Ab-positive kidneys (Arm 2A), and standard of care kidney transplants (Arm 2B).
2. The number and percentage of subjects with clinical outcomes while on the

waitlist (SAEs, delisting from waitlist, death) among subjects who receive an HCV RNA-positive kidney in Arm 1 and among those subjects who do not receive a study eligible HCV RNA-positive kidney (all Arm 2 subjects) overall and with breakdown by the category in Arm 2 (2A, 2B and 2C). In addition, the total number of inpatient hospital days while on waitlist in those who did receive a study eligible HCV RNA-positive kidney (Arm 1) and total inpatient hospital days in those who did not (Arm 2) overall and with breakdown by categories of Arm 2 will be summarized descriptively.

3. The number and percentage of subjects with the following clinical outcomes and data post-transplant as applicable: death, graft failure, acute allograft rejection, delayed graft function, ALT elevations > 5x ULN, and SAEs. The difference in the overall percentage of subjects with clinical outcomes and data post-transplant between Arm 1 and Arms (2A + 2B1 – 2B4) will be assessed by logistic regression with Arm as a factor and appropriate covariates to adjust for possible differences between Arms including waiting list priority, blood group, geographic region and sensitization as appropriate.

For subjects of Arm 1 and Arm 2A who become HCV infected, we will collect additional clinical outcomes of sclerosing cholestatic hepatitis and extrahepatic manifestations of HCV.

In additional analyses, G/P treatment-related severe adverse events, and G/P treatment-emergent Grade ≥ 3 laboratory values will be counted as clinical outcomes for subjects in Arm 1.

4. Additional allograft function outcomes for subjects post-transplant: mean eGFR over time and proteinuria.
5. Time to deceased donor kidney transplantation will be compared between all patients who enrolled in this MYTHIC trial and transplant candidates from the Organ Procurement and Transplantation Network (OPTN) database using a Cox

proportional hazards model; MYTHIC participants will be matched 1:3 to OPTN patients on demographics and characteristics known to influence waiting time including waiting list priority, blood group, geographic region, and sensitization.

6. In addition, for subjects in study Arm 2A receiving HCV RNA-negative/HCV Ab-positive kidneys, the rate of HCV transmission will be summarized.

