4.2 Secondary Objectives

The secondary objectives are:

- 1) Among all subjects enrolled in the study, to describe time to kidney transplant and cumulative incidence of each type of transplant: a study-eligible HCV RNA-positive kidney (Arm 1), a study-eligible HCV RNA-negative/HCV antibody-positive kidney (Arm 2A), or a kidney transplant performed as part of standard of care treatment (Arm 2B).

2) To describe clinical outcomes while on the waitlist after consent (Serious Adverse events [SAEs], delisting from waitlist, death) between those who receive a study-eligible HCV RNA-positive kidney (Arm 1) and in subjects consented for this study who do not receive a study-eligible kidney transplant from an HCV RNA-positive donor (all Arm 2 subjects) overall and with breakdown by the 3 categories of Arm 2 as below:

A: subjects who receive a kidney from a study-eligible HCV RNA-negative/HCV Ab-positive donor

B: subjects who receive a standard of care kidney transplant

C: subjects who were not transplanted within 1 year of consent

Hereafter, these categories will be referred to as Arms 2A, 2B and 2C.

A “standard of care” transplant will be defined as any of the following kidney transplants: a deceased donor HCV RNA-positive kidney transplant that did not meet donor criteria for Arm 1 or HCV RNA-positive kidney transplant that place after last transplant allowed for Arm 1 but met criteria for Arm 1 inclusion (2B1); a deceased donor HCV RNA-negative/HCV Ab-positive kidney transplant that either did not meet donor criteria or took place > 6 months after the last Arm 1 transplant (2B2); a deceased donor HCV RNA-negative/HCV Ab-negative transplant at a MYTHIC clinical site (2B3); any living donor kidney transplant at a MYTHIC clinical site (2B4); or any kidney transplant at a different center than the 7 clinical sites (2B5).

In addition, to compare the total number of inpatient hospital days while on the waitlist and after study consent in those who did receive a study eligible HCV RNA-positive kidney (Arm 1) vs total inpatient hospital days in those who did not (Arm 2) overall and with breakdown by the 3 categories of Arm 2 (2A, 2B and 2C).

3) To describe clinical outcomes and data post-transplant (death, graft failure, acute allograft rejection, delayed graft function, estimated glomerular filtration rate [eGFR], proteinuria, ALT elevation > 5 times the upper limit of normal (ULN), SAEs)

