8.1.4 Secondary Clinical Outcomes

Secondary clinical outcome analyses will be performed for subjects prior to kidney transplant in both Arms 1 and 2, and post kidney transplant for those who receive a kidney transplant in Arms 1 and 2. For details on safety reporting and periods of safety reporting see section 6.1.4.

The cumulative incidence function curves of time to kidney transplant will be created for each type of kidney transplant (Arms 1, 2A, 2B), and cumulative incidence and standard error (SE) will be calculated for each type of kidney transplant.

An exploratory analysis will create cumulative incidence function curves of time to kidney transplant for the subgroups of Arm 2B if sufficient subjects are enrolled in Arm 2B.

The number and percentage of subjects with clinical outcomes while on waitlist and after study consent (SAEs, delisting from waitlist, death) among subjects who receive an HCV RNA-positive kidney (Arm 1) and among those subjects who do not receive an HCV RNA-positive kidney (all Arm 2 subjects) overall and with breakdown by category of Arm 2 (2A, 2B, 2C). In addition, the total number of inpatient hospital days while on waitlist in those who did receive an HCV RNA-positive kidney (Arm 1) and total inpatient hospital days in those who did not (Arm 2) overall and with breakdown by category of Arm 2 will be summarized descriptively with mean, median, standard deviation (SD), minimum and maximum.

We will match MYTHIC trial participants 1:3 to comparators derived from the Organ Procurement and Transplantation Network database. Matching will be based on demographics and baseline characteristics known to influence waiting time, including waiting list priority, blood group, geographic region, and sensitization. A comparison of time to kidney transplantation between the kidney transplant candidates enrolled in the MYTHIC trial and OPTN comparators will be performed using a Cox proportional hazards model.

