Summary of Statistical Analysis Plan for MYTHIC Study

[Draft: April 26, 2020]

Part	Patient Group(s)	Outcome	Statistical Analysis ^a
1	Arm 1 (ITT)	SVR12	- estimated probability of SVR12 and 95% confidence interval (CI) - exact binomial calculations
2	Arm 1 (ITT)	Virologic failure (VF)	- estimated probability of SVR12 and 95% confidence interval (CI) - exact binomial calculations
3	Arm 1 (ITT)	Post-treatment virologic relapse	- estimated probability of SVR12 and 95% confidence interval (CI) - exact binomial calculations
4	All patients	HCV-viremic kidney transplant (KT); i.e., Arm 1 KT	- cumulative incidence and 95% CI - death and other KT types treated as competing risk - estimate non-parametrically, using Lin (1997) which proceeds through the cause-specific hazards, or Fan (2013) which uses Inverse Probability of Censoring Weighting (IPCW).
5	All patients	Non-HCV-viremic KT; i.e., Arm 2A-2B KT	- same as for component (4).
6	All, by Arm	Hospital admissions	- Arm treated as a time-dependent treatment - crude hospitalization rate per 100 patient-years (PY) and 95% CI - use robust variance estimator, to account for correlation among hospital admissions within-patient
7	All, by Arm	Hospital admissions	- Arm treated as a time-dependent treatment - proportional rates model (Lin et al., 2000) - robust SEs, to account for clustering within-patient
8(a)	All, and SRTR* controls	Kidney transplant	- exclude, from SRTR, all patients who indicated consent to receive an HCV-viremic KT (hereafter: SRTR*) - estimate prognostic score using SRTR* patients: KT as event - 1:5 matching (MYTHIC : SRTR*) based on prognostic score with caliper - Cox regression, with MYTHIC as lone covariate, stratified by matched set

8(b)	All, and SRTR* controls	Kidney transplant	Same as 9(a), but using exact matching on small set of predictors, with prognostic score used to break ties among potential matches
9	Arm 1 – ITT	Compliance	Treated as repeated binary (0/1) data, with 1 indicating compliance (i.e., having taken 80-120% of prescribed pills)
10	Arm 1 – ITT	Death	Time to event; Cox regression
11	Arm 1 – ITT	Graft failure	Time to event; Cox regression
12	Arm 1	Delayed graft function	DGF: binary (0/1) response. Compute OBS/EXP, where OBS=observed number of DGFs for Arm 1 and EXP= expected count based on logistic regression model fitted to HCV-negative UNOS patients from large academic centers

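### Synopsis secondary endpoint 1 limits time to transplant and cumulative incidence to subjects who were transplanted, contradicting objective 1 and the draft SAP (minor)

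*Protocol*

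**What the plan says.** The protocol synopsis (Statistical Methods, Clinical endpoints, item 1) gives the population and measure as "Among all subjects enrolled in the study who receive a kidney transplant, the time to kidney transplant and cumulative incidence" for three kinds of transplant: Arm 1, Arm 2A and Arm 2B.

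The objective this endpoint serves has a different population. Section 4.2, item 1, reads "Among all subjects enrolled in the study, to describe time to kidney transplant and cumulative incidence of each type of transplant", and the synopsis states the objective in the same way. The enrolled cohort includes Arm 2C, defined in section 4.2 as "C: subjects who were not transplanted within 1 year of consent".

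Section 8.1.4 opens by planning pre-transplant analyses in Arms 1 and 2, and post-transplant analyses in recipients. It then plans cumulative incidence curves of time to transplant for Arms 1, 2A and 2B, without saying who is in the denominator.

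The SAP, marked as a draft of April 2020, lists all patients as the group for Part 4 (Arm 1 transplant) and Part 5 (Arm 2A and 2B transplant), with "death and other KT types treated as competing risk".

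**The concern.** A cumulative incidence describes what happens to everyone at risk. If the analysis set is restricted to subjects who had the event, nobody is censored and nobody dies or is delisted before transplant. Two things follow. The incidences for Arms 1, 2A and 2B are forced to a total of about 100% by the end of follow-up, whatever the true access to transplant. Time to transplant is also shortened, because subjects who waited through follow-up without a kidney contribute no waiting time.

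The endpoint is meant to show how likely a consenting candidate is to receive each type of kidney, and how soon. Computed on recipients only, it shows the mix of kidney types among those transplanted, which is a different quantity and would overstate access if read as the first.

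**Working it through.** **Inputs**
- Enrolled: up to 90 (synopsis, number of subjects).
- Arm 1 transplants: target 30 (same place).
- Total transplants: at least 40 of 90, given as 44%, over an estimated 6 months (section 8.2).

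**Step 1. Reproduce the plan's figure.** 40/90 = 44.4%, which agrees with the stated 44%. The documents give no planning figure for endpoint 1 itself; this is the nearest.

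**Step 2. Compare the two denominators.** Let T be the number transplanted by the end of follow-up, with 30 of them in Arm 1. Assume nobody is lost before the end, so that simple proportions equal cumulative incidences.
- As written: Arm 1 = 30/T; any transplant = T/T = 100%.
- All enrolled: Arm 1 = 30/90; any transplant = T/90.

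| T | Arm 1, as written | Arm 1, all enrolled | Any, as written | Any, all enrolled |
|---|---|---|---|---|
| 40 | 75.0% | 33.3% | 100% | 44.4% |
| 50 | 60.0% | 33.3% | 100% | 55.6% |
| 60 | 50.0% | 33.3% | 100% | 66.7% |
| 70 | 42.9% | 33.3% | 100% | 77.8% |
| 80 | 37.5% | 33.3% | 100% | 88.9% |
| 90 | 33.3% | 33.3% | 100% | 100% |

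The two versions agree only if all 90 are transplanted.

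**Step 3. Look before the end of follow-up.** If everyone is followed to a common end, the recipients-only curve is the all-enrolled curve divided by its final value: F(t)/F(end). An illustrative simulation used 90 subjects, 12 months of follow-up and 1,000 runs. Its assumptions, which are not in the documents, were a transplant rate giving about 44% at 6 months, a 75/10/15 split across Arms 1, 2A and 2B, and death or delisting at 0.5% per month.

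| Sum over the three types | All enrolled | Recipients only |
|---|---|---|
| 6 months | 0.440 | 0.649 |
| 12 months | 0.677 | 1.000 |

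The formula gives 0.440/0.677 = 0.650 at 6 months, in line with the simulated 0.649. So the total is below 100% before the end, but it is already inflated. Time to transplant shifts as well: half of the recipients-only group is transplanted before 6 months, whereas among all enrolled that point comes after 6 months.

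**Step 4. Check that the three types cover every transplant.** Arm 2B takes in transplants outside the study criteria and at other centers, so coverage is nearly complete. Two small gaps remain: eligible antibody-positive kidneys beyond the Arm 2A maximum of 20, and those falling between 24 weeks (the Arm 2A limit in section 5.1) and 6 months (the 2B2 threshold) after the last Arm 1 transplant. Hence about 100%, not exactly 100%.

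**Step 5. Set the texts against each other.** Objective 1 and SAP Parts 4 and 5 use everyone enrolled. Death before transplant can compete with transplant only if untransplanted subjects are in the analysis set, so the SAP method cannot work as intended on the synopsis population. The synopsis endpoint is the outlier.

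**The case against.** The strongest reply is that this is a stray clause and no analysis section plans to act on it. Section 8.1 sends analysis details to the SAP, and the SAP, dated after the October 2018 synopsis, has the right population and competing risks. Section 8.1.4 opens with pre-transplant analyses in both arms, which together are all enrolled subjects, and attaches the restriction to recipients only to post-transplant outcomes. Since time to transplant is a waitlist outcome, both arms is the natural reading. This stands and is the reason the point is minor. It does not remove the contradiction: an endpoint definition is operative text, section 8.1.4 still names no denominator for the curves, and the SAP is marked draft.

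Several stronger readings are tempting but unsupported:
- *That the synopsis is the protocol's only guide to the population.* The opening of section 8.1.4 points to both arms.
- *That this is the trial's only measure of access.* Synopsis endpoint 5, section 8.1.4 and SAP Part 8 also compare time to transplant for all enrolled patients with matched registry candidates.
- *That 75% against 33% is the expected error.* It is one end of a range. It sets a whole-study target of 30 against a floor of 40 transplants planned over about 6 months, while Arm 2 is followed for at least a year.
- *That everyone with a long wait is dropped.* Long waiters transplanted during follow-up stay in; only those never transplanted in follow-up leave.

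**Conclusion.** The contradiction is real and its severity is minor. Followed literally, synopsis endpoint 1 yields a distribution of kidney types among recipients, with a total fixed near 100% at the end of follow-up. The Arm 1 figure would be overstated by between 0 percentage points (all 90 transplanted) and about 42 points (75.0 − 33.3, with 40 transplanted), assuming 90 enrolled, 30 Arm 1 transplants and complete follow-up. A reader might infer that the trial will report inflated access. The documents do not support that, because the draft SAP specifies the right population. What they support is that the protocol's endpoint definition disagrees with its own objective and with the SAP, and should be corrected so that no table is built from it.

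**What to change.** In synopsis endpoint 1, delete the clause that limits the population to transplant recipients, so that the item opens as objective 1 does. In section 8.1.4, state that the curves for Arms 1, 2A and 2B use all enrolled subjects, with time counted from enrollment and with death and the other transplant types as competing events, as in the SAP. Keep the three types separate there: SAP Part 5 pools Arms 2A and 2B, whereas objective 1 asks for each type. The SAP does not list delisting as a competing event, so the same sentence could say how it is handled.

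The cost is one deleted clause and one added sentence in the next amendment. Waitlist deaths and delistings are already collected for all subjects, so no new data are needed, and the SAP's population does not change.
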